7. STUDY ASSESSMENTS AND PROCEDURES

Protocol waivers or exemptions are not allowed with the exception of immediate safety concerns. Adherence to the study design requirements, including those specified in the Time and Events Table, are essential and required for study conduct.

Time and Events Tables are provided for subjects receiving randomized treatment ([Table 6](#)) and for subjects who permanently discontinue randomized treatment ([Table 7](#)). Because Hgb levels become more variable with increased time between dialysis sessions,

the designated study visit should occur during the dialysis session with the shortest interval from the previous session.

Designated study visits for subjects in the screening period or study treatment period who have not yet initiated dialysis can occur on any day of the week.

Designated study visits for subjects on dialysis should be scheduled as follows from the screening assessment to the end of the study:

- For subjects on 3X/week HD: The designated study visit must not occur on the first dialysis session of the week. For example, if on a Monday-Wednesday-Friday schedule, the study visit should be on Wednesday or Friday.
- For subjects on 2X/week HD: The visit should occur during the session that is closest to the previous HD session. For example, if a subject receives dialysis on a Monday and Thursday, the study visit should be on the Thursday (2 days from the previous dialysis session) rather than the Monday (3 days from the previous dialysis session).
- For subjects on PD: study visits can occur on any day of the week.

Details regarding study-specific equipment are provided in [Appendix 7](#).

Post-randomization visits should be referenced back to the Randomization visit (Day 1). The visit window for those on randomized treatment for the Week 2 and Week 4 visits is ± 3 days. The visit window specified for those on randomized treatment from Week 6 onwards is ± 1 week. However, to ensure continuity of randomized treatment, study visits should be no more than 5 weeks apart. In exceptional circumstances, minor changes to visit structure may be permitted after consultation with the PPD/GSK Medical Monitor.

Study assessments should preferably be done at dialysis centers, however, in some circumstances assessments can be performed at the research site.

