7.1. Time and Events Tables and Procedures for Subject Follow-up

Table 6 TIME AND EVENTS TABLE FOR SUBJECTS ON RANDOMIZED TREATMENT

Protocol activity (visits ± 1 week, except Weeks 2 and 4 which are ± 3 days)	Screening Week -2 ¹	Randomization (Day 1)	Weeks 2, 6	Full study visit Weeks 4, 16, 28, 40	Abbreviated study visit Weeks 8, 12, 20, 24, 32, 36, 44, 48	Week 52	Unscheduled	Follow-up Weeks 56-58
Written informed consent ¹⁹	X							
IRT system	X	X	X	X	X		X	X
Entry criteria	X	X						
History: medical, hospitalization, transfusion; demography, height	X							
Weight and estimated dry (target) weight	X	X	X	X	X	X	X	X
SBP/DBP ² , HR ²	X	X ² (triplicate)	X	X	X	X ² (triplicate)	X	X
ECG ³	X	X						
Ultrasound of kidneys and adrenal glands	X ⁴							
Randomized treatment dispensing ¹⁶		X		X	X		X ^{5,6}	
Randomized treatment compliance ¹⁶			X	X	X	X	X ⁷	
Iron therapy, transfusions (record in eCRF, if applicable)		X	X	X	X	X		X
Rescue medication (record in eCRF, if applicable)			X	X	X	X		X
Females only: estradiol & FSH (if required)	X							
Serum pregnancy test ⁸ (FRP only)	X	X		X	X ¹⁷	X	X	X
HemoCue Hgb	X	X	X	X	X	X	X	
Hematology ⁹	X	X		X	Hgb only	X	X	X
Clinical chemistry ⁹	X	X		X		X	X	X
Ferritin, serum iron, UIBC	X ¹	X		X		X		X
Vitamin B12 ¹ , folate	X							
Hepcidin		X		X		X		X

Protocol activity (visits \pm 1 week, except Weeks 2 and 4 which are \pm 3 days)	Screening Week -2 ¹	Randomization (Day 1)	Weeks 2, 6	Full study visit Weeks 4, 16, 28, 40	Abbreviated study visit Weeks 8, 12, 20, 24, 32, 36, 44, 48	Week 52	Unscheduled	Follow-up Weeks 56-58
iPTH		X		X		X		X
Storage biomarkers ¹⁸		X		Wk 28		X		
Kt/V _{urea} for dialysis adequacy ¹⁰				X		X		
Lipids (non-fasting), direct LDL		X				X		
PK Sampling ¹¹				Weeks 4, 8, 12 ¹¹				
Genetics sample ¹²		X						
hsCRP		X		Week 28 only		X		
EQ-5D-5L & VAS ¹³ , SF-36 ¹³		X		Weeks 8,12, 28 only		X		
CKD Anemia Symptoms Questionnaire (CKD-AQ) ^{13,14} , PGI-S ¹³	X	X		Weeks 8,12, 28 only		X		
PGI-C ¹³				Weeks 8,12, 28 only		X		
Healthcare resource utilization (subject reported)	X	X	X	Weeks 4,8,12,16, 20, 24, 28 only		X		X
Hospitalization / kidney transplant (record in eCRF, if applicable)			X	X		X		X
Non-serious AEs, SAEs, AEs of Special Interest, clinical events	X ¹⁵	X	X	X	X	X	X	X
Review concomitant medications	X	X	X	X	X	X	X	X

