10.4.1.2. Treatment States for CV Endpoint Data

Treatment State	Definition
Pre-Treatment	Date < Treatment Start Date
On-Treatment	Treatment Start Date ≤ Date ≤ Last Non-Zero Dose Date + 28 days
Post-Treatment	Date > Last Non-Zero Dose Date + 28 days
Post-Randomization	Randomization Date ≤ Date

NOTES:

- If the last non-zero dose date is missing and the treatment start date is non-missing and Date ≥ Treatment Start Date, then the assessment will be considered to be On-Treatment
- Treatment state definitions use the imputed CV endpoint date

10.4.1.3. Treatment States for BP, Lipid Parameters, Clinical Chemistry, Hematology, Other Laboratory Tests, Hepatobiliary (Liver) and Vital Signs Data

Treatment State	Definition
Pre-Treatment	Date ≤ Treatment Start Date
On-Treatment	Treatment Start Date < Date ≤ Last Non-Zero Dose Date + 1 day
Post-Treatment	Date > Last Non-Zero Dose Date + 1 day
Post-Randomization	Randomization Date < Date

NOTES:

- If the last non-zero dose date is missing and the treatment start date is non-missing and Date > treatment start date, then the assessment will be considered to be On-Treatment

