10.4.1.4. Treatment States for AE Data

AEs are to be recorded on the eCRF from the start of randomization treatment until the Follow-up visit, at the timepoints specified in the Time and Events table from Section 10.2.1. Serious AEs assessed as related to study participation or related to a GSK product are to be reported on the eCRF from the time a subject consents to participate in the study

CONFIDENTIAL

201410

up to and including any follow-up contact. AE of worsening of an on-going event will be counted once in a particular treatment state.

Treatment State	Definition
Pre-Treatment	
 For subjects with a non-missing screen failure date, if AE onset is on or before the screen failure date: AE Start Date \leq Screen Failure Date For randomized subjects with a missing treatment start date, all AEs are considered pre-treatment For randomized subjects with a non-missing treatment start date, if AE onset date is before treatment start date: AE Start Date $<$ Treatment Start Date
Post-Randomization	
If AE onset date or AE worsening date is on or after the randomization date Randomization date \leq AE Start Date Randomization date \leq AE Worsening Date AE worsening during post-randomization will be defined relative to the maximum intensity of AE prior to randomization date.
 
AE worsening date is the first date in the post-randomization period, when AE intensity increased relative to the maximum intensity of the AE prior to randomization date.

Treatment emergent	
If AE onset date or AE worsening date is on or after treatment start date & on or before the last non-zero dose date plus 1 day. Treatment Start Date \leq AE Start Date \leq Last Non-Zero Dose Date + 1 day Treatment Start Date \leq AE Worsening Date \leq Last Non-Zero Dose Date + 1 day AE worsening during treatment emergent will be defined relative to the maximum intensity of AE prior to randomized treatment start date.
 
AE worsening date is the first date in the treatment emergent period, when AE intensity increased relative to the maximum intensity of the AE prior to randomized treatment start date.

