Follow-up	
If AE onset date or AE worsening date is after the last non-zero dose date plus 1 day. AE Start Date $>$ Last Non-Zero Dose Date + 1 day AE Worsening Date $>$ Last Non-Zero Dose Date + 1 day AE worsening during follow-up will be defined relative to the maximum intensity of AE prior to randomized treatment start date.
 
AE worsening date is the first date in the follow-up period, when AE intensity increased relative to the maximum intensity of the AE prior to randomized treatment start date.

Onset /Worsening Time Since 1 st Dose (Days)	
If Treatment Start Date $>$ AE Onset Date: AE Onset Date - Treatment Start Date If Treatment Start Date \leq AE Onset Date: AE Onset Date - Treatment Start Date + 1 If Treatment Start Date $>$ AE Worsening Date: AE Worsening Date - Treatment Start Date If Treatment Start Date \leq AE Worsening Date: AE Worsening Date - Treatment Start Date + 1 Missing otherwise.

Onset /Worsening Time Since Last Dose (Days)	
If Last Non-Zero Dose Date \leq AE onset date: AE onset date – last non-zero dose date + 1 If Last Non-Zero Dose Date $>$ AE onset date: AE onset date – last non-zero dose date

CONFIDENTIAL

201410

Treatment State	Definition
	If Last Non-Zero Dose Date \leq AE worsening date: AE worsening date – last non-zero dose date + 1 If Last Non-Zero Dose Date $>$ AE worsening date: AE worsening date – last non-zero dose date Missing otherwise.
Duration (Days)	AE Resolution Date – AE Onset Date/AE Worsening Date + 1
Drug-related	If relationship is marked 'YES' on eCRF or if the value is missing.

NOTES:

- AEs that occur or worsen during interruptions of randomized study treatment will be classified as treatment emergent and post-randomization.
- If the last non-zero dose date is missing and the treatment start date is non-missing and the AE onset date or AE worsening date is on or after the treatment start date, then the AE will be considered to be treatment emergent.
- If AE onset date or AE worsening date is missing and AE resolution date is before the treatment start date, then the AE will be classified as Pre-treatment.
- If AE onset date or AE worsening date is missing and AE resolution date is either missing or on or after treatment start date, then the AE will be classified as treatment emergent and post-randomization.

10.4.1.5. Treatment States for Concomitant Medications (Other Than IV Iron Dose Endpoints and Iron Use Summaries)

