Pre-treatment medications are those taken (i.e., started) before the start date of randomized treatment. On-treatment medications are those taken (i.e., started or continued) at any time between the randomized treatment start date and the last non-zero dose date + 1 day, inclusive. Pre-treatment medications that were continued during this on-treatment period are also considered to be on-treatment medications. Post-treatment medications are those taken (i.e., started or continued) at any time after the last non-zero dose date + 1 day. On-treatment medications that were continued during this post-treatment period are also considered to be post-treatment medications. Post-randomization medications are those taken (i.e., started or continued) at any time on or after the randomization date.

It will be assumed that the medication has been taken on the date in which it is reported as started or stopped. Also, for any medication starting on the same date as randomized treatment, it will be assumed that the medication was taken after the subject started taking randomized treatment.

Illustrations of the pre-treatment, on-treatment, and post-treatment treatment states are included below:

CONFIDENTIAL

201410

	Pre-treatment	On-treatment			Post-treatment	Pre-treatment medication	On-treatment medication	Post-treatment medication
		Randomized Treatment Start Date	Last Non-zero Dose Date + 1 Day	Last Non-zero Dose Date + 2 Days				
(a)	x—x					Y	N	N
(b)	x—		—x			Y	Y	N
(c)	x—		—	—x		Y	Y	Y
(d)		x—x				N	Y	N
(e)		x—			—x	N	Y	Y
(f)					x—x	N	N	Y
(g)	?—x					Y	N	N
(h)	?—		—x			Y*	Y	N
(i)	?—		—		—x	Y*	Y*	Y
(j)	x—		—		—?	Y	Y**	Y**
(k)		x—			—?	N	Y	Y**
(l)					x—?	N	N	Y
(m)	?—		—		—?	Y***	Y***	Y***
(n)	x—	x				Y	Y	N
(o)	?—	x				Y*	Y	N
(p)		x	—x			N	Y	N
(q)		x	—	x		N	Y	N
(r)				x	—x	N	Y	Y
(s)				x	—?	N	Y	Y**
(t)				x	—x	N	N	Y
(u)				x	—?	N	N	Y
(v)		x—	—	x		N	Y	Y

x = start/stop date of medication

? = missing start/stop date of medication

* If a medication is stopped On-treatment or Post-treatment and no start date is recorded it will be assumed that the medication was ongoing from the Pre-treatment phase

** If a medication is started Pre-treatment or On-treatment and no stop date is recorded then usage will be assumed to be ongoing for the remainder of the study

*** If a medication has no start or stop date it will be assumed that the medication was ongoing from the Pre-treatment phase to the Post-treatment phase

CONFIDENTIAL

201410

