
Last Non-Zero Dose Date
 
 • Date of last actual dose of randomized study treatment from IP Discontinuation eCRF form. 
 ○ The dose steps used by the dosing algorithm described in the protocol include a dose hold or a zero dose. If subjects are assigned by the algorithm to a zero dose, they do not receive randomized treatment for that period. Hence, it would be possible for a subject to complete the study, while still following the dosing algorithm, but not actually be taking any actual randomized treatment. The last non-zero dose date, then captures the latest date in the study that a subject physically took a dose of randomized treatment. • The eCRF allows for the possibility of partial or missing dates to be recorded for the last actual dose of randomized study treatment on the IP Discontinuation form (i.e., missing day, or day and month, or day and month and year). In such a case, or in case of subjects who have a non-missing treatment start date, but are missing an IP Discontinuation form, the following conventions will be applied in order to impute a last non-zero dose date: 
 ○ Missing day: 
 ▪ The last day of the month will be used, unless the treatment stop date also occurs in the same month; in this case, the treatment stop date will be used. ○ Missing day and month; 
 ▪ ‘31’ will be used for the day and ‘Dec’ will be used for the month, unless the treatment stop date also occurs in the same year; in this case the treatment stop date will be used. ○ Missing day, month, and year: 
 ▪ Treatment stop date will be used only for subjects who have a non-missing treatment start date.

CONFIDENTIAL

201410

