
Treatment Stop Date
 
 • Calculated as the latest randomized treatment dose stop date for subjects who have a non-missing treatment start date. Note that this date could come from a randomized treatment exposure record with a missing or partial dose stop date if the associated dose start date for that exposure record is on or after the last non-missing randomized treatment dose stop date. • The eCRF allows for the possibility of missing or partial dates to be recorded for the dose stop date on the study treatment form (i.e., missing day, or day and month, or day and month and year). In such a case, the following conventions will be applied in order to impute a treatment stop date: 
 ○ Missing day: 
 ▪ The last day of the month will be used, unless the study completion or withdrawal date also occurs in the same month; in the case, the study completion or withdrawal date will be used. ○ Missing day and month: 
 ▪ '31' will be used for the day and 'Dec' will be used for the month, unless the study completion or withdrawal date also occurs in the same year; in this case, the study completion or withdrawal date will be used. ○ Missing day, month and year: 
 ▪ The study completion or withdrawal date will be used only for subjects who have a non-missing treatment start date.

End of Treatment Value
 
 • Only defined for subjects with a non-missing treatment start date • Hgb, iron, transfusion and PRO parameters: the latest value on or before the treatment stop date + 1 day. • Blood pressure, central laboratory, and vital signs parameters: the latest value on or before the last non-zero dose date + 1 day.

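### AE, blood pressure and laboratory windows close one day after the last physical dose in both arms, so on the planned calendar every darbepoetin Week 52 visit counts as off-treatment

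*SAP*

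**What the plan says.** SAP 10.4.1.4 closes the treatment-emergent AE window "on or before the last non-zero dose date plus 1 day". SAP 10.4.1.3 ends the on-treatment state for BP, lipids, chemistry, hematology, other laboratory tests, liver tests and vital signs at "Last Non-Zero Dose Date + 1 day". The end-of-treatment value in SAP 10.6.1 follows suit: "Blood pressure, central laboratory, and vital signs parameters: the latest value on or before the last non-zero dose date + 1 day". SAP 10.4.1.5 uses the same date for concomitant medications: "at any time between the randomized treatment start date and the last non-zero dose date + 1 day, inclusive". None of these rules has an arm-specific version.

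SAP 10.6.1 explains that the last non-zero dose date "captures the latest date in the study that a subject physically took a dose of randomized treatment". Its stated reason is dose holds; injection intervals are not mentioned. AEs between doses are protected by one note: "AEs that occur or worsen during interruptions of randomized study treatment will be classified as treatment emergent and post-randomization". That note does not reach past the final dose.

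Other data types have other windows. Cardiovascular endpoints run to last non-zero dose + 28 days (SAP 10.4.1.2). Hemoglobin, iron, transfusion and patient-reported data use treatment stop date + 1 day (SAP 10.4.1.1).

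Daprodustat is taken daily (Protocol 6.1). Darbepoetin is injected every 4 weeks, every 2 weeks or weekly (Protocol 12.3.1). Protocol Table 6 shows no dispensing at Week 52.

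**The concern.** A + 1 day allowance suits a daily tablet. For an injection meant to act for 7, 14 or 28 days, it ends the window near the start of the final interval, and a darbepoetin subject who completes the trial as planned is off-treatment at the last visit.

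Four outputs depend on it.

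- **Week 52 BP.** Both mixed-model runs listed in SAP 8.2.1.2 use on-treatment values only. The missing-at-random assumption stated there concerns subjects who permanently discontinue, not completers removed by a date rule. Table 8 footnote 1 promises an analysis of all available values, and 8.2.1.2 states its missing-data assumption, but no such run is listed.
- **Lipids.** While a subject is on treatment, Week 52 is the only scheduled post-baseline sample, and the displays in SAP 8.2.2.2 use on-treatment values.
- **End-of-treatment values.** The two arms would be read at different visits.
- **Fatal SAEs and AEs leading to discontinuation.** SAP 8.2.3.2 tabulates treatment-emergent events. An event that prevents the next injection falls in the excluded part of the interval unless it starts within a day of the last one.

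**Working it through.** The plan gives no figure to reproduce, so this is calendar arithmetic on its rules. Count days from randomization: Week 48 = 336, Week 52 = 364. A visit is on-treatment if its day is at most last dose + 1.

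**Planned calendar.** Dosing every I days, none on the Week 52 day: last dose = 364 − I, window end = 364 − I + 1, days lost = I − 1.

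| Regimen | Last dose | Window ends | Week 52 on-treatment | Days lost |
|---|---|---|---|---|
| Daprodustat daily | 363 | 364 | yes | 0 |
| Darbepoetin weekly | 357 | 358 | no | 6 |
| Darbepoetin 2-weekly | 350 | 351 | no | 13 |
| Darbepoetin 4-weekly | 336 | 337 | no | 27 |

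**Visit variation.** Protocol 7 allows ± 1 week and says "study visits should be no more than 5 weeks apart". Week 48 can fall on days 329-343 and Week 52 on days 357-371, giving 15 × 15 = 225 pairs. A gap of g days occurs in 15 − |g − 28| pairs. Removing gaps of 36-42 days (7+6+5+4+3+2+1 = 28 pairs) leaves 197. Pairs are weighted equally, and injections run every I days from the Week 48 visit; both are assumptions.

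With dosing continued on schedule and no injection on the Week 52 day, the visit qualifies only on the day after an injection:

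- 4-weekly: gap 29, 14 pairs; 14/197 = 7%.
- 2-weekly: gaps 15 and 29, 2 + 14 = 16; 16/197 = 8%.
- Weekly: gaps 15, 22 and 29, 2 + 9 + 14 = 25; 25/197 = 13%.

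If an injection on the visit day is allowed, gaps equal to a multiple of I also qualify:

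- 4-weekly: 14 + 15 = 29 (15%).
- 2-weekly: 16 + 1 + 15 = 32 (16%).
- Weekly: 25 + 1 + 8 + 15 + 8 = 57 (29%).

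If injections stop after 28 days of supply, the counts are 0, 2 and 11 for 4-weekly, 2-weekly and weekly dosing, or 0, 3 and 20 with a visit-day injection (0-10%). The same limit on tablets would leave daprodustat on-treatment only for gaps up to 28 days: 1 + 2 + … + 15 = 120 of 197 (61%).

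**Scheduled on-treatment post-baseline values in a completer, planned calendar (Protocol Table 6).** Chemistry and full hematology are taken at "Full study visit Weeks 4, 16, 28, 40" and at Week 52.

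| Measure | Daprodustat | Darbepoetin | End-of-treatment visits compared |
|---|---|---|---|
| BP | 15 | 14 | Week 52 v Week 48 |
| BP model without stabilization period | 7 | 6 | not applicable |
| Chemistry, hematology other than Hgb | 5 | 4 | Week 52 v Week 40 |
| hsCRP | 2 | 1 | Week 52 v Week 28 |
| Lipids | 1 | 0 | Week 52 v none |

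**Ordinary AEs in completers.** Assume a constant hazard and a true one-year incidence of 30%. The share shown is 1 − 0.7^((365 − (I − 1))/365). With exponents 338/365, 352/365 and 359/365 this gives 28.1%, 29.1% and 29.6% for 4-weekly, 2-weekly and weekly dosing.

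**The case against.** The strongest reply is that most of what matters is protected. All-cause mortality, MACE and hospitalization are analyzed in the ITT population from randomization to study completion, with later reported deaths included (SAP 10.6.4.1). Combined on- and off-treatment BP summaries are planned (8.2.1.2), and the iron and vital-sign tables of potential clinical importance include post-treatment values. The AE and laboratory tables are descriptive, the BP tests are nominal, and AE person-time is cut at the same date. All of this stands and limits the severity. It does not restore the Week 52 on-treatment BP contrast or the lipid display. Matching person-time does not recover an event that itself ends dosing.

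Three stronger readings are tempting, and the documents do not support them.

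- **That the Week 52 BP contrast cannot be estimated.** This needs an empty darbepoetin cell. It is empty on the planned calendar, but only sparse once visits vary.
- **That the AE under-count can be quantified.** For an event after which no further dose is given, with uniform onset, 2 of I days are covered: 2/28 = 7%, 2/14 = 14%, 2/7 = 29%. The share of fatal or discontinuation events of this kind is not in the documents. Nor is capture on daprodustat complete, since dose holds and interruptions can precede death or stopping there too.
- **That the main AE window should be last dose plus one dosing interval.** In early stoppers that counts up to 28 days on darbepoetin against 1 day on daprodustat, including time after other anemia therapy has begun. It reverses the asymmetry in the roughly 30% whom Protocol 9.2.1 allows to stop before Week 28.

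**Conclusion.** The point holds and should be fixed. The rule is explicit, and on the planned calendar it makes the Week 52 visit off-treatment at every darbepoetin frequency and on-treatment for daprodustat. With visit variation and continued dosing, 7-13% of darbepoetin Week 52 visits count (15-29% with visit-day injections). Those percentages rest on equal weighting of visit days and on injections anchored at Week 48. The lower 0-10% range needs a 28-day supply limit that the documents do not state.

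The Week 52 BP contrast, a secondary endpoint without multiplicity adjustment, would have few or no darbepoetin values, and the on-treatment lipid comparison almost none. Fatal and discontinuation AE tables lose darbepoetin events by an unknown amount. A reader might infer that this flatters daprodustat, but the loss lowers the comparator's counts and so works against the test drug. Ordinary AE percentages in completers change little. Values after a terminal dose hold, and most values from the Early Treatment Discontinuation visit, are lost in both arms. Primary, principal secondary, cardiovascular, hemoglobin, iron, transfusion and patient-reported analyses are not affected.

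**What to change.** 1. In SAP 10.4.1.3 and the BP, laboratory and vital-signs line of the end-of-treatment value (10.6.1), add: 'For subjects who did not permanently stop randomized treatment before Week 52, the scheduled Week 52 visit, within its protocol visit window, is on-treatment.' This also keeps Week 52 values for subjects on a dose hold in either arm. Align the end-of-treatment BP-medication count (8.2.2.2), the concomitant-medication window (10.4.1.5), and the BP exacerbation person-time and model offset (10.6.4.2, 8.2.1.2).
2. In 10.4.1.4, for the same subjects, run the treatment-emergent window and its person-time to the Week 52 visit, and align 10.6.4.3 and 10.6.4.6.
3. For subjects who stop early, keep + 1 day as the main rule. Add supportive tables of fatal, discontinuation and all AEs at last dose + one assigned dosing interval, and at last dose + 28 days in both arms. State that the dosing-interval version counts up to 28 days on darbepoetin against 1 day on daprodustat, including events after other anemia therapy begins.
4. List in 8.2.1.2 the mixed model on all available (on- and off-treatment) BP values that Table 8 footnote 1 promises. This corrects a separate mismatch and is needed whatever window is chosen.

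The cost is SAP wording, reprogramming of flags and person-time, and extra tables that need explanation. No new data are needed: AEs are collected to the Follow-up visit and Week 52 values are already scheduled. No dose or clinical rule changes.
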